 - during invasive ventilation and NIV: ventilation mode, inspiratory tidal volume (V_{TI}) (L), total respiratory rate (RR), fraction of inspired oxygen (FiO_2) (%), positive end-expiratory pressure (PEEP) (cm H₂O), saturation of

arterial oxygen (SpO_2) (%), partial pressure of arterial oxygen (PaO_2) (kPa), and position (supine or prone)

- during HFNO: FiO_2 (%) air flow (L/min), SpO_2 (%), PaO_2 (kPa), and position (supine or prone)

Definitions

Day 1 and Day 2 are the first two complete calendar days of ICU admission and have a duration of 24 hours (from 00:00 to 23:59). Day 0, defined as the time between ICU admission and 23:59 of that day, is ignored.

Endpoints

The primary endpoint is the amount of oxygen used per minute at patient level.

The secondary endpoints are the total amount of oxygen used and the amount of oxygen used per hour at patient level.

The supplemental oxygen per minute ($Supplemental\ Oxygen_{min}$) is calculated every 2 hours. For invasive ventilation and NIV

$$Supplemental\ Oxygen_{min}\ (L) = V_{Ti}\ (L) * total\ RR * (FiO_2 - 0.21)$$

For the HFNO group

$$Supplemental\ Oxygen_{min}\ (L) = air\ flow\ (L/min) * (FiO_2 - 0.21)$$

Supplemental oxygen per hour ($Supplemental\ Oxygen_{hour}$) and total supplemental oxygen on Day 1 and 2 are calculated using the area under the curve (AUC) method.

Statistical analysis plan

Continuous data are reported as medians with interquartile ranges and categorical data as numbers with percentages.

Each patient is assigned to a group named 'invasive ventilation or NIV' and 'HFNO' based on the first used form of ventilatory support, meaning that patients who received HFNO first and invasive ventilation or NIV afterwards is included in the 'HFNO' group and vice versa.

To assess differences between patient groups in both approaches, Wilcoxon-Mann-Whitney test for continuous data and Fisher exact test for categorical data is used. Differences between demographic data, chronic comorbidities and SAPSII are shown in Table 1. Supplemental oxygen per minute (Supplemental Oxygen_{min}) at patient level in the two groups is compared using the Wilcoxon-Mann-Whitney. Cumulative frequency distribution of supplemental oxygen per minute are shown for the two groups.

Supplemental oxygen per minute is compared with repeated measures analysis of variance (ANOVA). If significant, a pairwise comparison between every time points is performed.

Sankey diagrams are used to show the different ventilatory support devices used during Day 1 and Day 2.

Supplemental oxygen per hour (Supplemental Oxygen_{hour}) and total supplemental oxygen in the two groups is compared using the Wilcoxon-Mann-Whitney test. Distribution graphs are used to show the differences between the two groups.

In one sensitivity analysis, patients who received both HFNO and invasive ventilation or NIV on Day 1 and Day 2 are excluded, so that patients who received

exclusively HFNO are included in the 'HFNO' group and patients who received only invasive ventilation or NIV are included in the 'invasive ventilation or NIV' group. For this second approach Baseline characteristics are shown in Table 3.

All analyses are conducted in R Studio v. 4.0.3 (R Foundation, Vienna, Austria) and significance level is set at 0.05.

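### The endpoints are called oxygen used, but the formulas give oxygen above room-air content: 79% of the oxygen added for the counted flow if a pure source is blended with room air

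*SAP*

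**What the plan says.** The Endpoints section of the SAP states: "The primary endpoint is the amount of oxygen used per minute at patient level". It continues: "The secondary endpoints are the total amount of oxygen used and the amount of oxygen used per hour at patient level". The Objectives and Hypothesis sections use a slightly different term, supplemental oxygen used.

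The working definition follows in the same section. For invasive ventilation and NIV it is inspiratory tidal volume × total respiratory rate × (FiO2 − 0.21). For HFNO it is the air flow times the same bracket ("L/min) * (FiO_2 - 0.21"). Hourly supplemental oxygen "and total supplemental oxygen on Day 1 and 2 are calculated using the area under the curve (AUC) method".

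Under Data collected, FiO2 is recorded as a percentage ("during HFNO: FiO_2 (%) air flow (L/min"), whereas the formulas need a fraction.

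The Statistical analysis plan section puts these quantities on an absolute scale in three places: "Continuous data are reported as medians with interquartile ranges"; "Cumulative frequency distribution of supplemental oxygen per minute are shown for the two groups"; and, for the hourly and total amounts, "Distribution graphs are used to show the differences between the two groups".

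The SAP does not say in words that the endpoint is oxygen above room-air content. It does not state the purity of the oxygen source or how gas is blended.

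**The concern.** Flow × (FiO2 − 0.21) is a coherent quantity, but it is not the amount of oxygen added to the gas. Adding oxygen to a fixed total flow displaces room air, and with it the oxygen which that air carried. Subtracting 21% of the whole flow therefore removes more than the room air in the blend contributed. The clearest case is FiO2 1.0: the blend holds no room air, yet 21% of the flow is still subtracted.

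What is at stake is the size of the reported litres. A reader who takes the medians, distributions and totals as oxygen used, which is what the endpoint sentences call them, would take away figures that are too small. This matters most for anyone using the hourly or total litres to judge supply.

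**Working it through.** The SAP gives no numerical result for these endpoints, so there is no figure to reproduce. The check is a mass balance.

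**Inputs.** From the SAP: the two formulas, room-air fraction 0.21, and 48 hours of observation (Day 1 and Day 2, 24 hours each, so 2,880 minutes). Assumed: pure source oxygen blended with room air. The flows and FiO2 values below are illustrative and are not in the SAP.

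**Derivation.** Let F be the counted flow (tidal volume × rate, or HFNO flow), f the FiO2 as a fraction, O the source oxygen and A the room air.

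- Volume: O + A = F
- Oxygen: O + 0.21A = fF
- Substituting A = F − O: 0.79·O = F(f − 0.21), so O = F(f − 0.21)/0.79

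The SAP formula gives F(f − 0.21) = 0.79·O at every FiO2 above 0.21, in both groups. The correction factor is 1/0.79 = 1.266.

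**Numbers.** HFNO at 60 L/min and FiO2 1.0: the SAP formula gives 60 × 0.79 = 47.4 L/min, against 60.0 L/min added.

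At FiO2 0.60 the bracket is 0.39:

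| Counted flow | Measure | SAP formula | Oxygen added |
|---|---|---|---|
| HFNO 50 L/min | L/min | 19.5 | 24.7 |
| | L per hour (×60) | 1,170 | 1,481 |
| | L over 48 h (×2,880) | 56,160 | 71,089 |
| Ventilator 10 L/min | L/min | 3.9 | 4.9 |
| | L per hour | 234 | 296 |
| | L over 48 h | 11,232 | 14,218 |
| Difference | L per hour | 936 | 1,185 |
| | L over 48 h | 44,928 | 56,871 |
| Ratio | | 5.0 | 5.0 |

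The area under the curve is linear in the per-minute values, so the factor passes unchanged into the hourly and total endpoints.

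**Source purity.** With source purity p, the source gas needed is F(f − 0.21)/(p − 0.21) and the oxygen in it is p times that. The SAP value is then (p − 0.21)/p of the oxygen added: 0.790 at p = 1.00, 0.774 at p = 0.93 and 0.767 at p = 0.90. The shortfall is 21% to about 23% over this assumed range.

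**Effect on the tests.** Dividing every value by the same positive constant leaves all ranks unchanged, so the Wilcoxon-Mann-Whitney result is unchanged. It multiplies every sum of squares in the ANOVA by the same number, so the F ratios are unchanged. Both formulas carry the same factor, so this also holds for patients who switch device. On simulated data (100 per group, 12 time points) the Mann-Whitney p-value and the F statistics for group, time and their interaction were identical before and after division.

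**The case against.** The strongest reply is that the SAP labels the formula output supplemental oxygen, and uses that term in the objective, the hypothesis and the analyses. Supplemental can fairly be read as oxygen beyond what air supplies. On that reading the formulas are exact, nothing is understated, and only two endpoint sentences are loosely worded. This stands in part: it is why renaming the endpoints is an acceptable remedy. It does not clear the plan as written. The endpoint sentences, which say what is to be reported, drop the qualifier, and supplemental oxygen used can as readily mean oxygen added from the supply, of which the formula returns 79%.

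A second reply is that no planned inference changes. That is correct, and it limits the severity.

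Three stronger readings might be inferred, and the SAP does not support them:

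- **That the group comparison is biased.** The factor is common to both formulas and cancels in the tests and ratios. This needs the same source purity in both groups, and the SAP suggests no difference.
- **That all litres are 21% below the total draw from the supply.** The 21% applies to the counted flow only. Tidal volume × rate leaves out any ventilator bias flow or uncaptured leak, and the SAP gives no figure for either. The ventilator shortfall against total draw is therefore unknown, as is the error in the group difference on that scale.
- **That oxygen used means all oxygen delivered, flow × FiO2.** The ratio would then vary with FiO2 and ranks could change: 12 L/min at 0.5 against 9 L/min at 0.6 gives 6.0 against 5.4 L/min delivered, but 3.48 against 3.51 by the SAP formula. Subtracting 0.21 shows that the SAP does not intend this quantity.

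**Conclusion.** The point holds in a limited form. The endpoint names and the endpoint formulas describe different quantities. If the source is pure and blended with room air, the planned litres for the counted flow, and their absolute group differences, are 21% too low as a measure of oxygen used. The comparative conclusion is safe from this factor: tests and ratios of these values are unaffected, and the hypothesis sets no threshold in litres. Severity is modest, but the mismatch should be corrected because it sits in the definition of the primary and both secondary endpoints of a study about oxygen use.

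**What to change.** If oxygen used is the intended quantity, divide both formulas by 0.79, enter FiO2 as a fraction (it is recorded in %), state the pure source as an assumption, and carry the change into the hourly and total AUC endpoints.

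If excess over room air is intended, keep the formulas, define the quantity in words, name it so in the objective and endpoint sentences (for example, supplemental oxygen above room-air content), and do not report it as oxygen used.

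In either case add one sentence of limitation: the ventilator value, rescaled or not, covers the counted flow only and is not total draw from the supply.

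The cost is one constant in the code or a change of wording, plus that sentence. No new data are needed.
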